To achieve the aim of this study we will conduct a randomized controlled trial with three arms during May-Dec 2017. Participants will be Danish adults traveling on vacation in 2018 for a period of 1-3 weeks, recruited from the civil registration system. After enrollment and pretesting, participants will be randomly assigned to one of three experimental conditions. Three experimental groups will receive innovative intervention strategies for promoting sun protection practices during vacation – Protection Routine (1), Protection Routine (2) or both Protection Routine (1+2). The fourth experimental condition will be a minimal treatment control group. The primary outcomes of the trial will be a reduction in frequency of sunburn by adherence to the current sun protection advice from the Danish Cancer Society, i.e., use of shade, hats, protective clothing, and sunscreen as secondary outcomes. We hypothesize that the following two interventions will be able to reduce significantly the UVR exposure and risk of sunburns in Danes going on vacation to destinations with high UVI.

Protection routine 1

The existing evidence of sun protection against the detrimental effect of UV radiation shows that it is effective if performed correctly [26, 28]. We will develop a package of existing training and information and test if it will lead to better adherence. The package will include:

- The rationale of the prioritized sun advice [32]
- Activity planner, with suggestions to why a break from the sun is beneficial and how to plan activities before and after UVI maximum i.e. morning/early noon and afternoon/evening [32]
- Download of the UV-application ‘UVindeks’ for smartphones developed by the campaign and activating UV alert of geographic destination [33]
- A skin type guide

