- A newly developed instruction for correct application of sunscreen [40]

Denmark is not a hat-wearing society. By making smart design hats available and attractive may increase this sun protection behavior, which has large potential in prevention of skin cancer (**ibid: p2**). A very simple study showed that a brief instruction to sunscreen application increased the provided protection significantly [40].

Protection routine 1+2

The group will receive both above mentioned interventions and will reveal potential dose response effects from level of protection.

Control group

All groups including the control group will receive a minimal intervention with the current sun advice from the Danish Sun Safety Campaign.

Study population

The participants of the study are recruited from the Danish civil registration based system. The study population will represent all groups of the Danish population. Eligibility criteria for the project are persons living in Denmark going on vacation in May-December 2018 and having a smartphone compatible with either apple iOS (version 7.0 or newer) or Google Android (version 4.0 or newer). The period May to December is chosen as it includes all types of vacationers. The summer vacation constitutes the majority of the sunny vacations of the Danes. The period includes both the summer, where Danes typically travel to the Mediterranean area and the winter period where travel patterns change a bit to more exotic areas like Thailand, Egypt and the Canarias Islands. Exclusion criteria are persons younger than 18 years of age.

Randomization

The participants will be randomized to one of the intervention groups or to the minimal-treatment control group. The randomization procedure is described in the protocol.

Confounders

Possible confounders includes age, gender, education, skin type, skin cancer history, nevi, sun-seeking behavior and number of sunny vacations in past 5 years [28].

Statistical methods and power calculations

The number of completing participants (n= 1.980) is based on a power calculation, recruitment for similar studies conducted by the applicant [41, 42] and our recent pilot study (unpublished, summarized in the end of this application).

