A statistical power calculation shows that this sample size yields 95 % probability to detect a 10-percentage point drop from 50 % to 40 % in sunburn between an intervention group and the control group, and 80 % probability to detect a 7-percentage point drop from 50 % to 43 %. Our pilot study showed a 17-percentage point difference between our participants (32 %) relative to our annual sun surveys (49%). The number of invited participants to reach a final sample of ~2000 are included in the flow diagram in the protocol.

To obtain the final study sample size, we assumed 25 % of Danes invited to participate will volunteer for the project [41], >80 % will use of interventions (unpublished pilot study) and > 90 % will complete questionnaire [41, 42]. Loss to follow up after one year is expected to be 25 % according to travel patterns with high continuity of the Danes.

Multiple logistic regression analysis will be applied for analysis of differences in sunburn fraction. Analysis of variance will be used to analyze differences in sun protection score and UVR exposure score. Alpha criterion will be p=0.05 (two-tailed).

Intention-to-treat analysis will be applied by using multiple imputation by chained equations to account for missing information on sunburn among non-responders, using PROC MI in SAS 9.3. The imputation procedure includes variables hypothesized to potentially predict missing information (age, sex, education, skin type, sun behaviour, sun protection, sun intentions and intervention group). Analyses will be repeated including responders only and counting non-responders with same sunburn fraction as responders in the control group.

Clustering within families is not included in the planned analysis as it is unlikely to influence the results because participants from the same family have very low odds of being drawn with a total of 30.000 drawn out of the entire Danish population 18+ (app. 4.3 million).

Evaluation by validated questionnaire

Sun protective behavior, exposure to UVR and sunburn will be evaluated by use of a questionnaire validated by personal electronic UV-measurements [7, 43, 44]. This newly developed survey tool has made it possible in this project to evaluate the skin cancer interventions, without tracking of development of skin cancer which can take several years to develop after excessive UVR exposure. The short time period from intervention to evaluation minimizes recall bias.

Success criteria

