majority of the elements in intervention 1. The feasibility of intervention 2 was previously shown [42, 61]. Ninety-three percent received and read the material. At posttest, we showed a sunburn rate in the study population, which was 17 percentage points lower than reported for our annual survey of the Danish population. All intervention elements (Sun advice, smartphone application, sunscreen application guide, skin type guide) proposed in this study were considered relevant and useful by more than 80 % of those who completed the pilot study. The skin type guide scored lowest with 81 % and the app scored highest with 95 % among those who had it available (google android and apple ios phones; not available for windows phones for instance). Furthermore, we saw a 9-percentage point increase in use of sunscreen, while use of long-sleeves and hat was largely unchanged. The hats proposed for the study, were not tested in the pilot, however the feasibility of the hat was previously tested in minor interventions. We also show a slight increase in knowledge of the UV Index in the population survey from 89 % to 93 % in the pilot test.

Potential pitfalls

Albeit highly unlikely, we have sketched various scenarios that could influence the project.

The project is based in the Danish Cancer Society, which means that during the project period, should any of the applicants change job, be long term absent/sick or likewise, qualified researchers of same level will replace them.

The project involves products from third part companies, which can be prone to internal or external structural changes or bankruptcy, leaving them no possibility to deliver a given product. In any case, an equally qualified product will be sought in replacement.

The recruitment method is register based. Should the Danish Civil Registry for some reason not be able to deliver data, like sudden legal changes in person data handling or likewise, other methods of recruitment are available.

All potential changes to the project will of course be reported to funder immediately.

Protocol

Time Schedule

Mar-Apr 2018	Planning of intervention & evaluation	Registering trial Ordering sample from civil registry system Preparation of interventions Preparation of information and homepage
Apr-May 2018	Recruitment and scheduling;	Sending invitations Ordering products for intervention Baseline Questionnaire

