The evaluation will be conducted in the online survey system, SurveyXact, provided by Rambøll. The system is used in numerous evaluations of the Danish Cancer Society. The evaluation is based on the validated UV behavior questionnaire recently developed by Danish Sun Safety Campaign. The questionnaire will be adapted to the trial.

[figure not shown]
Preparation of interventions

An intensive intervention package was developed prior to the study. The package is composed by known elements from the Danish Sun Safety campaign. The package also includes download of the UV-App developed by the Danish Sun Safety Campaign. The app includes an alert function for high UV-Indexes and can be adapted to the correct location by GPS or a selected city around the world. This mobile app is fully developed and available for this trial. The participants randomized to the package will receive alerts to take precautions against solar UVR before and during their vacation.

Invitations

The invitations for the project will be handled (printed, enveloped and sent) by trained volunteers from the Danish Cancer Society. Participants will sign up for the project on a developed web-page of the project. On the project homepage the participants will fill in a short form of contact information, demographic information, departure and arrival dates of their upcoming vacation and baseline sun behavior information for non-responder analyses. Participants who have not yet planned their vacation are instructed to contact the project team

Flow Diagram

once they have planned it. Likewise they will be reminded every 2-3 weeks during the period by mail or phone. Repeated invitations will be sent after two and four weeks to non-responders. Afterwards, participants will be contacted by the volunteers by phone to confirm their participation and receive information about the study. A student will be dedicated in organizing workflow of the volunteers and participate in the training of the volunteers. We have good experiences with this procedure from other projects like www.mituv.dk and www.statusd.dk also funded by TrygFonden.

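### No stated model uses earlier sunburn, and the plan does not say whether the baseline questionnaire asks about it; the comparison stays valid but forgoes a cheap predictor

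*Combined protocol and SAP*

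**What the plan says.** **Baseline data.** Under Invitations, the web form collects contact and demographic information, "departure and arrival dates of their upcoming vacation and baseline sun behavior information for non-responder analyses". Two other places point to further baseline collection. Intervention study says: "After enrollment and pretesting, participants will be randomly assigned to one of three experimental conditions". The Time Schedule lists a "Baseline Questionnaire" for April–May 2018. Neither gives its items.

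**Instrument.** Evaluation by validated questionnaire says: "Sun protective behavior, exposure to UVR and sunburn will be evaluated by use of a questionnaire". It does not say whether sunburn is asked at baseline, after the trip, or both. It names sunburn separately from behaviour and exposure.

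**Models.** Statistical methods and power calculations says: "Multiple logistic regression analysis will be applied for analysis of differences in sunburn fraction". That sentence fixes no covariates. The nearest list is under Confounders: "Possible confounders includes age, gender, education, skin type, skin cancer history, nevi, sun-seeking behavior and number of sunny vacations in past 5 years". The imputation variables are "age, sex, education, skin type, sun behaviour, sun protection, sun intentions and intervention group". Randomisation is stratified by gender, age group and region (Main study). Earlier sunburn is in none of these lists.

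**Success measure.** Success criteria compares intervention groups with control after the intervention; it is not a change from baseline.

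**The concern.** Whether a person burned on an earlier sunny trip is a natural predictor of whether they report a burn on the next one. It combines skin sensitivity, habits and the person's own threshold for calling something a burn. The last of these matters for a self-reported outcome: the protocol itself says that sunburn is under-reported by self-evaluation and that people overestimate what their skin tolerates. Skin type and behaviour items do not measure that threshold directly.

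Two things are at stake. The first is power: outcome variation that could have been explained stays in the comparison. The second is the imputation, on which the intention-to-treat analysis rests. It works best with variables that predict both the outcome and reply. If reply depends on sunburn history differently by arm, a model without that history can correct only as far as its other variables stand in for it.

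**Working it through.** **1. The plan's own power.** Inputs: 1,980 completers, 50% v 40% (95% power stated), 50% v 43% (80% stated), two-sided 0.05. The text describes both three arms and a fourth condition, so both equal splits are tried.

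Power = Φ{[Δ√n − 1.96√(2p̄(1−p̄))] / √(p₁(1−p₁)+p₂(1−p₂))}.

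- Four arms, 1,980/4 = 495. For 50% v 40%: (0.1×22.249 − 1.379)/0.700 = 1.208, power 88.7%. For 50% v 43%: (0.07×22.249 − 1.383)/0.704 = 0.249, power 59.8%.
- Three arms, 1,980/3 = 660: 95.5% and 72.3%.

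Neither split reproduces both stated figures. The lower base, 495 per arm, is used below.

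**2. Adjusting for earlier sunburn alone.** The documents give no link between earlier and later sunburn, so odds ratios of 2, 4 and 8 are assumed. Previous sunburn is set at 49%, the annual-survey figure in the power section. For each odds ratio, find the risks q₀ (not burned before) and q₁ (burned before) that average to the arm's rate m. Then R² = 0.49×0.51×(q₁−q₀)²/[m(1−m)], averaged over the two arms, and effective n = 495/(1−R²). This is an approximation on the risk-difference scale.

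| Odds ratio | q₀, q₁ at m = 50% | q₀, q₁ at m = 40% | Mean R² | Effective n | Power 50 v 40 | Power 50 v 43 |
|---|---|---|---|---|---|---|
| none | – | – | 0 | 495 | 88.7% | 59.8% |
| 2 | 0.416, 0.588 | 0.319, 0.484 | 0.029 | 510 | 89.5% | 61.1% |
| 4 | 0.337, 0.670 | 0.244, 0.563 | 0.109 | 555 | 91.9% | 64.8% |
| 8 | 0.266, 0.744 | 0.177, 0.632 | 0.222 | 636 | 94.9% | 70.9% |

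The last column recomputes R² with m = 43%.

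The protocol also reports 27% sunburned on sunny vacations in 2014. With 27% in place of 49%, R² is 2.3 / 8.7 / 17.4% and power for 50% v 40% is 89.4 / 91.3 / 93.7%.

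**3. Gain beyond terms the plan already lists.** Assume the listed covariates explain 5–10% of outcome variance and earlier sunburn adds 1–5%.

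- 50% v 40%: from a 5% base, 495/0.95 = 521 gives 90.2%. Adding 1% (495/0.94 = 527) gives 90.5%; adding 5% (495/0.90 = 550) gives 91.6%. The gain is about 0.3–1.5 points.
- 50% v 43%: from a 5% base, 62.0% rises to 62.5% (adding 1%). From a 10% base, 64.4% rises to 66.9% (adding 5%). The gain is about 0.5–2.5 points.

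**4. Differential reply, illustrative.** In the intervention arm only, assume 16% of those burned before and 4% of the others do not reply. Overall non-reply is 0.49×0.16 + 0.51×0.04 = 9.9%, near the planned maximum of 10%. Among responders, 0.49×0.84/0.901 = 45.7% were burned before, 3.33 points below 49%. The observed drop is inflated by 0.0333×(q₁−q₀):

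- odds ratio 2: 0.0333×0.165 = 0.55 points
- odds ratio 4: 0.0333×0.319 = 1.06 points
- odds ratio 8: 0.0333×0.455 = 1.52 points

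A true 10-point drop would appear as about 10.6, 11.1 or 11.5 points if nothing in the model stood in for sunburn history.

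**5. The same scenario under the planned sensitivity analysis.** The plan also repeats the analysis with non-responders given the control responders' sunburn fraction. The difference becomes 0.901 × the observed drop: 9.5, 10.0 and 10.4 points. The standard error of the difference at 495 per arm is √(0.25/495 + 0.24/495) = 3.1 points.

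**The case against.** A reader might infer that the primary outcome has no baseline value. The documents do not show that. A pretest precedes randomisation, a separate baseline questionnaire is scheduled, a baseline paper is planned, and the evaluation instrument covers sunburn. The wording about baseline sun behaviour could even be read to include it, although the plan elsewhere names sunburn separately from behaviour. What stands is that the item is unspecified and that, even if collected, it is in no listed model.

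A reader might also infer that the sunburn comparison is biased or unprotected. It is not: randomisation protects a between-group comparison made after the intervention, and no baseline value is needed for validity. Adjustment is a matter of efficiency.

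The sizes can fairly be challenged too. The table in step 2 compares adjustment with none, whereas the plan has a multiple logistic model with skin type, sun-seeking behaviour and past sunny vacations as candidate terms; step 3 is the fairer comparison. An older trip, often to another destination, weakens the association, and an odds ratio of 8 has no basis in the documents. The bias case ignores four imputation variables that plausibly track sunburn history (skin type, sun behaviour, sun protection, sun intentions), and the planned sensitivity analysis largely offsets it at odds ratios of 4 and 8 and slightly over-corrects at 2. It would therefore be too strong to say that the imputation cannot correct for such reply. Finally, in logistic regression, adjustment raises power but does not shrink the standard error of the conditional log odds ratio, so the gain should be described as power.

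All of this limits the size. None of it supplies the missing item or model term.

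**Conclusion.** The point holds as a gap in specification with a modest cost. Whether earlier sunburn is recorded is not stated, and none of the listed covariates, imputation variables or stratification factors includes it. The step 2 gains, up to 94.9% and 70.9% power at an odds ratio of 8, are the most to expect under the assumed range. About 0.3–2.5 points is the likelier gain once skin type and behaviour terms are in the model. The 0.6–1.5 points of bias are an upper case that assumes reply differs fourfold by sunburn history in one arm only, before the plan's own safeguards act; they are at most about half a standard error.

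The prevalence, odds ratios, variance shares and reply pattern are assumptions, and 495 per arm assumes four equal arms. The case for acting is that the change is nearly free and that, on either equal split, unadjusted power for the 7-point drop is below the stated 80%.

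**What to change.** State whether the pretest or baseline questionnaire records earlier vacation sunburn. If it does, use that answer. If not, add one item to the sign-up form, before randomisation so that allocation cannot influence the answer: sunburned on the most recent sunny vacation – yes / no / no such vacation in the past 5 years. Then, under Statistical methods and power calculations, pre-specify this three-category variable as a term in the logistic model for sunburn and add it to the imputation variables.

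The cost is one web-form question and two lines of analysis text. The drawbacks are imperfect recall of an older trip and a third category for people without one.

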While it is hoped that all individuals will use the interventions, research by our team and others have found that exposure to interventions typically vary across participants. Exposure to the interventions will be measured by post-test questionnaire. Also, use of the mobile app will be assessed by registering when downloaded from a link sent by email and text-message reminders to the participants. Automated email and text-message reminders will be considered as tools to increase use of the mobile app and the personal dosimeter. Completion of the full intervention will be defined as follows: control group - having received the minimal intervention materials; Protection Routine 1- use of 50 % or more of the intervention materials in the package; Protection Routine 2 – . However, we will also analyze the amount of use of the interventions for the impact of intervention exposure on intervention effectiveness.

Data collection and handling

Data collection is executed by an electronic questionnaire sent immediately after return from the vacation. If unanswered reminders are sent after 4 days, 9 days and 14 days. The data collection methods follows results of a recent validation study, which showed that validity of the questionnaire answers is crucially dependent on short time from exposure to answering the questionnaire. Responses within 2 weeks of return from vacation were valid.

1-year-follow-up

Participants that have completed the intervention are invited to a follow up study the following year. The procedure is similar to the initial procedure. Only now, participants are invited by e-mail (supported by phone) and screened for possible vacation to a sunny destination. Participants going on a sunny vacation will receive a questionnaire immediately after return from the vacation for evaluation of long-term effects.

1. Bray, F., et al., *Global estimates of cancer prevalence for 27 sites in the adult population in 2008*. Int.J.Cancer, 2012.

2. Engholm, G., et al., *NORDCAN: Cancer Incidence, Mortality, Prevalence and Prediction in the Nordic Countries, Version 5.1. Association of Nordic Cancer Registries*. Danish Cancer Society. 2012.
3. Armstrong, B.K. and A. Kricker, *How much melanoma is caused by sun exposure?* Melanoma Res., 1993. **3**: p. 395-401.
4. Gandini, S., et al., *Meta-analysis of risk factors for cutaneous melanoma: II. Sun exposure*. Eur.J.Cancer, 2005. **41**(1): p. 45-60.

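### The 1-year follow-up invites those who completed the intervention, a post-randomisation condition that, on the plan's written definition, differs between control and Protection Routine 1

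*Combined protocol and SAP*

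**What the plan says.** The 1-year-follow-up section reads "Participants that have completed the intervention are invited to a follow up study the following year". Those invited are then "screened for possible vacation to a sunny destination", and those who travel receive a questionnaire "for evaluation of long-term effects". The Time Schedule gives the follow-up its own manuscript, the third.

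The Completion of intervention section, just above, defines completion of the full intervention arm by arm: "control group - having received the minimal intervention materials; Protection Routine 1- use of 50 % or more of the intervention materials". The rule for Protection Routine 2 cannot be read in the available text, so nothing is claimed here about that arm or the combined arm. The same section says "Exposure to the interventions will be measured by post-test questionnaire"; app downloads are also registered.

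Under Main study, randomisation follows agreement to participate, and packages arrive before departure. The section on statistical methods plans an intention-to-treat analysis with multiple imputation of sunburn for non-responders. It also says "Loss to follow up after one year is expected to be 25" per cent, and ties this to travel patterns.

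**The concern.** Receiving, using and reporting on materials all happen after allocation, so a follow-up restricted to completers is selected after randomisation. How much that matters depends on what completing means.

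- **Arm-specific reading (the written definition).** Control participants qualify by delivery, Routine 1 participants by behaviour. Low users drop out of one arm and stay in the other. If low users burn more or less often than users, the 1-year difference shifts even when the intervention has no lasting effect. Use is measured mainly by the post-test questionnaire, so qualifying in Routine 1 largely requires an answer as well, whereas receipt in control need not.
- **Common reading.** The Success criteria and the pilot summary use completion for finishing the study. The rule is then the same in every arm. A shift arises only if response rates, or the kind of person who responds, differ by arm.

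The planned imputation is for non-responders. It is not stated to cover the follow-up or people who were never invited. What is at stake is the claim about long-term effects.

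**Working it through.** The plan states no figure for this bias, so there is none to reproduce. What follows is an illustration with assumed inputs.

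**Inputs from the plan.** "The number of completing participants (n= 1.980"); ">80 % will use of interventions (unpublished pilot study) and > 90 % will complete questionnaire"; 25 % one-year loss; 50 % sunburn; two-sided 5 % test. The pilot summary reports that 93 % received and read the material.

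**Assumptions.** Four equal arms (the text says three in places but describes four groups). The completion share c in Routine 1 is 80 %, 90 % or 93 %; the plan's 80 % is a floor for use of the interventions, and the pilot's 93 % is not the 50 % rule either. The gap d in sunburn risk between non-completers and completers is 5, 10 or 20 points. There is no true effect and no covariate adjustment.

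**Numbers.** Working back through the plan's rates, 1,980 / (0.80 × 0.90) = 2,750 randomised, or 687.5 per arm. Response of 0.90 is held equal in both arms, so that only the use rule differs. Control at 1 year: 687.5 × 0.90 × 0.75 = 464. Routine 1: 464 × c = 371, 418 or 432.

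**Formulas, arm-specific reading.** Spurious difference b = (1 − c) × d. SE = √(0.25/n0 + 0.25/n1). Rejection rate = P(Z > 1.96 − b/SE) + P(Z < −1.96 − b/SE).

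Example: c = 0.80, d = 0.20 gives b = 0.04; SE = √(0.25/464 + 0.25/371) = 0.0348; b/SE = 1.15; rejection rate 0.21.

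| c | n0 vs n1 | b in points (d = 5, 10, 20) | rejection rate |
|---|---|---|---|
| 80 % | 464 vs 371 | 1, 2, 4 | 6 %, 9 %, 21 % |
| 90 % | 464 vs 418 | 0.5, 1, 2 | 5 %, 6 %, 9 % |
| 93 % | 464 vs 432 | 0.35, 0.7, 1.4 | 5 %, 5.5 %, 7 % |

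**Sensitivity of the 21 % to arm size.** Starting from 1,980 / 4 = 495 per arm less 25 % (371 vs 297) it is 18 %. If control non-responders also enter (687.5 × 0.75 = 516 vs 371) it is 22 %.

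**Common reading.** b = (difference in non-response) × d. With equal response and the same kind of non-responder, b = 0. With assumed response of 90 % in control and 85 % in Routine 1, b = 0.05 × d = 0.25, 0.5 or 1 point. With 464 vs 438, the rejection rate is about 5 % to 6 %.

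**The case against.** **The text does not bar non-completers.** It says completers are invited; it does not say only they are. That is so, but no other route is described. The flow diagram is not shown and could not be checked.

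**The definition may not govern invitations.** It concerns the full intervention, stands under a different heading, and is followed by a plan to analyse amount of use. This stands: the arm-specific reading is likely, not certain.

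**The reach figure.** A reader might infer that the 18 % reach under Study population recruitment confirms the arm-specific rule, since 0.25 × 0.80 × 0.90 = 0.18. It does not. That product applies 80 % use to every arm, control included. Exempting control would give 687.5 × 0.90 + 3 × 687.5 × 0.72 = 619 + 1,485 = about 2,104 completers, not 1,980 (if the other three arms all carry the 80 %). The plan itself explains the 18 % without a use term: 8 % of the draw, with under half of Danes travelling (0.08 / 0.18 = 0.44).

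**The common reading is close to ordinary attrition.** Agreed: its illustrated effect is negligible, and it needs a response imbalance that the documents do not suggest.

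**Planned adjustment.** The plan specifies multiple logistic regression and lists confounders such as skin type and sun-seeking behaviour. Adjustment could reduce the bias, so the rates above may overstate the error of the planned analysis. It would not restore the randomised comparison.

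**Modest importance.** The 1-year comparison is not among the success criteria, and the fix leaves selection on travelling again. Both are true, and both limit the weight of the point.

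**Conclusion.** The concern holds in a limited form. The described route into the 1-year follow-up is a post-randomisation condition. On the only written definition it differs between control and Protection Routine 1, so their long-term comparison would not be a randomised one. On the other reading the rule is common to all arms and any effect is likely to be small.

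The documents give no sunburn data by use or by response, so neither size nor direction can be derived. The illustrated range on the arm-specific reading is 0.35 to 4 points and a false-positive rate of about 5 % to 21 %, unadjusted and with assumed completion shares and risk gaps. A reader might take 21 % as the expected error rate. It is not: it needs both the 80 % floor and a 20-point gap, which is twice the plan's 10-point target effect. Every other case in the table is about 9 % or less. Nor does the point reach the primary post-vacation result; only the follow-up and its manuscript are affected.

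**What to change.** Change the sentence so that all randomised participants are invited to the 1-year follow-up, regardless of use of materials or response to the first questionnaire. Analyse by allocated arm, and keep the completers-only comparison as a labelled secondary analysis. Report by arm the numbers invited, screened, travelling, and with unknown travel status. State that the comparison remains conditional on a sunny vacation taken in the follow-up year: open invitation removes the first selection step, not this one.

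The cost is a short protocol edit and some extra e-mail or phone invitations, using contact details already held. With 687.5 per arm, the arm-specific reading adds about 138 people in Routine 1 (687.5 × 0.20), or up to about 190 if entry now also needs a questionnaire response (687.5 × 0.28); the number in the other two intervention arms depends on their rule. The common reading adds about 69 per arm (687.5 × 0.10), 275 in all. The follow-up response rate will probably fall, because the added people were less engaged. Completers can still be picked out if everyone is invited, but people never invited cannot be recovered at analysis.
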